# 11.0 Privacy/Confidentiality Issues

Data and specimens will be coded and protected according to institutional policies and protocol. Blood samples will be run on the day that they are obtained, and will only be stored afterwards according to routine laboratory protocol. Any blood that is obtained with routine clinical care on admission to the pediatric ICU but not used for the study will be discarded in an appropriate biohazard container within 24 hours of when it was drawn. [name] will maintain a password-protected master key with protected health information, and each patient case/medical record will have a unique identifier code and the master key will be the only link between the clinical records and the corresponding laboratory data. In addition, recorded patient identifiers (MRN, name, DOB) will be kept with the master key only. All other clinical data will be recorded in a

designated electronic data abstraction spreadsheet, which will be password-protected and separate from the patient identifiers and the key.

[figure not shown]
Vanderbilt, [name] and her staff will comply with any and all laws regarding the privacy of protected health information.

#### 12.0 Follow-up and Record Retention

The projected duration of the study is from the time of IRB approval through June 30, 2019.

Data will be stored in a password-protected RedCap database. Paper copies of the data will be kept to the absolute minimum. Only the PI and co-investigators will have access to the master patient key and patient identifiers during the study collection period. After the collection period, only the PI will maintain the master patient key for future study that may require linking clinical laboratory values with clinical data. The key will be maintained in the PI's office in the Section of Infectious Diseases at VUMC on a single password-protected hospital computer. Any paper copies or data on paper will be stored in a locked filing cabinet in the PI's office. Paper copies will be destroyed at the earliest possible time by being discarded in the hospital HIPAA-approved receptacles for PHI to be shredded according to hospital policy.

The PI, co-investigators and laboratory personnel will be appropriately trained to maintain the confidentiality and protection of PHI according to the study design and hospital practice.

#### Appendix A: Figure 1 – Procalcitonin-Guided Algorithm

Protocol Version # 9: Protocol Date: 3/27/19 Reference: Bouadma L et al. Use of procalcitonin to reduce patients' exposure to antibiotics in intensive care units (PRORATA trial): a multicenter randomized controlled trial. Lancet 2010; 375: 463-74

Exploratory objectives will be to evaluate the impact of a procalcitonin-guided antibiotic algorithm with antimicrobial stewardship guidance on adherence to the procalcitonin-guided algorithm, impact of procalcitonin-guided algorithm on antibiotic stewardship recommendations, impact on antibiotic use in a subgroups of patients with a diagnosis of pneumonia, patients who have antibiotics initiated due to concern for sepsis, patients with initial procalcitonin levels <0.5 ng/mL versus those with initial procalcitonin levels >0.5 ng/mL, patients without comorbidities, and patients admitted to the pediatric intensive care unit vs. those admitted to the pediatric cardiac intensive care unit.

DEFINITIONS

1. Antibiotic escalation: Changing to a broader spectrum antibiotic, addition of one or more antibiotics, or conversion of oral (PO) to intravenous (IV) route.

- 2. Antibiotic de-escalation: Changing to a narrower spectrum antibiotic, cessation of one or more antibiotics, or changing from an IV to PO route of appropriate drug.
- **3. Broad-spectrum antibiotic:** Vancomycin, daptomycin, amikacin, ceftazidime, cefepime, piperacillin/tazobactam, aztreonam, carbapenems
- **4. Antibiotic-associated complications**: Defined as rash, neutropenia, thrombocytopenia, acute kidney injury [defined as increase in serum creatinine >0.3 mg per dL or >1.5-fold from baseline, or urine output <0.5 mL per kg per hour for more than six hours], hepatotoxicity [defined as >2-fold increase in alanine aminotransferase, ALT, or conjugated bilirubin], or *C. difficile* infection
- **5. Multi-drug resistant organism:** Methicillin-resistant *S. aureus*, vancomycin-resistant *Enterococcus*, 3rd generation cephalosporin non-susceptible *Enterobacteriaceae*, multi-drug resistant *Pseudomonas aeruginosa* [resistant to aminoglycosides, cephalosporins, fluroquinolones, and carbapenems), carbapenem-resistant *Acinetobacter* and *Candida* spp. obtained from otherwise sterile sites [i.e. blood or urine cultures]

OUTCOME MEASURES

Primary Outcome Measures

1. Median days of therapy (DOT) per patient of antibiotic therapy (in days) within 14-days post randomization.

Secondary Outcome Measures

- 1. Median DOT per patient of broad-spectrum antibiotic therapy (in days) within 14-days post randomization.
- 2. Median time from randomization to first appropriate antibiotic escalation or de-escalation based on patient's clinical status and available supporting laboratory evidence, or lack thereof, of specific type of infection within 14-days post randomization.

Clinical Outcome Measures

- 1. In-hospital mortality within 30 days of randomization.
- 2. Length of stay in the hospital after randomization, up to 30 days, for those patients alive at 30 days. Length of stay will be date of discharge minus date of randomization.
- 3. Days in the ICU during hospitalization after randomization, up to 30 days, for those patients alive at 30 days.
- 4. Days spent using invasive ventilation methods (not including supplementary oxygen via nasal cannula or Vapotherm support) within 14-days post randomization.
- 5. Number of antibiotic-associated complications per patient within 14-days post randomization.
- 6. Acquisition of new hospital-acquired infections (HAIs) and/or multidrug resistant organisms (MDROs) within 30 days during index hospitalization identified on routine clinical or surveillance samples
- 7. Hospital re-admission within 30 days (yes/no)

Post Hoc Exploratory Analyses

- 1. Median DOT per patient of intravenous antibiotic therapy (in days) within 14-days post randomization
- 2. Antibiotic use > 72 hours (categorical) for any antibiotic, broad-spectrum antibiotics or IV antibiotics.
- 3. Count (%) of patients on 2 or more antibiotics at 24, 48, 72 and 96 hours after enrollment.
- 4. Total number of antibiotic stewardship recommendations made in each arm within 48-hours post randomization.

ProPICU: Statistical Analysis Plan

June 4, 2019

- 5. Rate of clinical provider compliance with adherence to suggested antibiotic escalation or de-escalation made by the antimicrobial stewardship team.
- 6. The primary endpoint will be analyzed comparing patients who:
 - Have antibiotics initiated due to concern for sepsis
 - Receive a clinical diagnosis of pneumonia
 - Have initial procalcitonin levels <0.5 ng/mL versus >0.5 ng/mL
 - Have no comorbidities versus those with comorbidities
 - Are in the pediatric intensive care unit at randomization
- 7. Number of antibiotic stewardship recommendations made in each arm within 48-hours post randomization will be analyzed (chi2 value will be compared between groups):
 - Male vs. female patients
 - Patients who receive a clinical diagnosis of pneumonia
 - Patients who have antibiotics initiated due to concern for sepsis
 - Patients who have initial procalcitonin levels <0.5 ng/mL versus >0.5 ng/mL

A. General Analysis Considerations

Data summaries and analyses will be presented by randomized arm.

To ensure participant confidentiality, listing of individual patient level data will be minimized as much as possible during study monitoring and for analyses. If such data are provided, they will be indexed with a unique blinded identifier or with identifiers removed. Study dates will not be presented, but provided as days/hours since randomization, as appropriate.

Participants who died prior to randomization, underwent bone marrow transplant or solid organ transplant prior to or after randomization, who are diagnosed with cystic fibrosis, or who ultimately are diagnosed with endocarditis, osteomyelitis, meningitis, mediastinitis or other invasive infection for which long duration of antibiotics is needed will be considered unevaluable for the primary outcome.

B. Statistical Monitoring Considerations

Routine statistical monitoring of accrual, study conduct, and data completion will be conducted by the statistical team and the study coordinator.

C. Monitoring Procalcitonin Algorithm Adherence

The study coordinator is responsible for monitoring intensive care unit provider adherence to the procalcitonin algorithm and, in the event of non-adherence, for soliciting reasons why they chose not to adhere to the algorithm.

D. Interim Analysis Considerations

The statistical team will perform an interim analysis when recruitment reaches 50% of goal accrual, to ensure safety of the procalcitonin-guided algorithm. Baseline characteristics such as age, sex and indication for antibiotics, primary outcome of overall DOT per patient within 14-days after randomization, and secondary outcomes of 30-day mortality and length of intensive care unit stay will be compared between groups.

E. Final Analysis Considerations

The primary analysis will be conducted when data from the last participant enrolled has been received.

The final analysis population will include participants who meet all eligibility criteria and no exclusion criteria.

The analysis will evaluate the primary, secondary, and exploratory outcomes in the procalcitonin-guided and control arms.

F. Analysis Plan

Statistical Considerations

Table summaries will present the following study population characteristics by randomized arm. All variables, as noted below, will be analyzed on the continuous scale or as categories or both as appropriate.

For continuous variables, summary statistics will include # of participants and median (Q1-Q3).

For categorical variables, summary statistics will include number (%) for each category. In calculation of percentages, participants with missing data will not be included in the denominator.

We will calculate the median days of antibiotic therapy per patient within the first 14-days post randomization in both treatment arms, together with the interquartile range. The primary test will be a Wilcoxon rank-sum test without the assumption of normality.

We will compare other continuous outcomes using a Wilcoxon rank-sum test, and categorical outcomes using a Pearson's chi-squared test.

We will perform a post-hoc analysis using a multivariable ordinal logistic regression model to assess the association between randomization group and the overall antibiotic duration of therapy per patient, adjusting for sex, recent surgical procedure, antibiotic indication of possible sepsis, and fever, vasopressor support and need for mechanical ventilation at enrollment.

We will perform a Cox proportional odds model adjusting for location of enrollment and study day to evaluate the hazard ratio for time to cessation of antibiotics within 4-days and within 10-days.

Final Analysis Considerations

The primary analysis will be a modified intention to treat (ITT) analysis. Participants who died prior to randomization, underwent bone marrow transplant or solid organ transplant prior to or after randomization, who are diagnosed with cystic fibrosis, or who ultimately are diagnosed with endocarditis, osteomyelitis, meningitis, mediastinitis or other invasive infection for which long duration of antibiotics is needed will be considered unevaluable. These are all issues that would otherwise qualify as exclusion criteria at the time of enrollment.

1. Study Population

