#### **Study Outcomes**

The **primary outcome** is days of antibiotic therapy in the first 14 days following randomization. **Secondary outcomes** are duration of broad-spectrum antibiotic therapy (defined as vancomycin, daptomycin, amikacin, ceftazidime, cefepime, piperacillin/tazobactam, aztreonam, carbapenems), time from randomization to first appropriate antibiotic modification (escalation or de-escalation), 30-day mortality, reinitiation of antibiotics for a bacterial infection within 30-days of antibiotic discontinuation, length of ICU stay, length of overall hospital stay, ventilator days, rates of antibiotic-

associated complications (i.e. rash, neutropenia, thrombocytopenia, acute kidney injury [defined as increase in serum creatinine  $\geq 0.3$  mg per dL or  $\geq 1.5$ -fold from baseline, or urine output < 0.5 mL per kg per hour for more than six hours], hepatotoxicity [defined as > 2-fold increase in alanine aminotransferase, ALT, or conjugated bilirubin], or *C. difficile* infection), infection with multi-drug resistant organisms (defined as methicillin-resistant *S. aureus*, vancomycin-resistant *Enterococcus*, 3rd generation cephalosporin non-susceptible *Enterobacteriaceae*, multi-drug resistant *Pseudomonas aeruginosa* [resistant to aminoglycosides, cephalosporins, floroquinolones and carbepenems], carbepenem-resistant *Acinetobacter*, and *Candida* spp obtained from otherwise sterile sites [i.e. blood or urine cultures]), cost of antibiotics from hospital billing data, and adherence to the PCT-guided algorithm.

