1.2 Study Population Characteristics

Table: Demographics

- a. Current age on day of study entry (in years): Continuous
- b. Sex at birth: By category (male/female)
- c. Self-reported race, ethnicity and race/ethnicity as defined by NIH reporting standards: By category

2. Health Characteristics/Status at Entry

- a. In pediatric ICU or pediatric cardiac ICU at randomization
- b. Requirement for intravenous vasopressor agents (categorical, yes or no)
- c. Mechanical ventilation (categorical, yes or no)
- Fever (temperature >38.0 deg F) or hypothermia (temperature <35.0 deg F) (categorical, yes or no)
- e. Surgical procedure within 2 weeks prior to enrollment (categorical, yes or no)
- f. Presence of comorbidity
 - Heart disease
 - Gastrointestinal disease
 - Neurologic disease
 - Bone/joint infection
 - Renal disease
 - Hematologic disease
 - Oncologic disease
 - Pulmonary disease
 - Other
 - No comorbidities
- g. Indication for antibiotics
 - Concern for sepsis
 - Pneumonia
 - Meningitis/encephalitis
 - Urinary tract infection
 - Other
- h. Attending physician on the day of enrollment

• Choose 1 of 20 pediatric ICU attending physicians who wrote the progress note for the patient on the day of enrollment

3. Antibiotic Use

Table: Days of antibiotic therapy per patient within 14 days (PRIMARY OUTCOME). Patients who are continued on antibiotics longer than 14 days will be assigned a time of 14 days per antibiotic.

Table: Days of broad-spectrum antibiotic therapy per patient within 14 days. Patients who are continued on broad-spectrum antibiotics longer than 14 days will be assigned a time of 14 days per antibiotic.

Table: Count (%) of patients on any antibiotic longer than 72 hours

Table: Count (%) of patients on broad-spectrum antibiotics longer than 72 hours

Table: Count (%) of patients on IV antibiotics longer than 72 hours

Table: Count (%) of patients on 2 or more antibiotics at 24, 48, 72, and 96 hours after enrollment

Table: Days of IV antibiotic therapy per patient within 14 days. Patients who are continued on IV antibiotics longer than 14 days will be assigned a time of 14 days per antibiotic.

Figure: Time to first antibiotic modification, using the empirical cumulative distribution function.

Figure: Percent of patients on antibiotics within 14 days of enrollment, using a Cox proportional hazards model

4. Sensitivity and Additional Analyses of the Primary Endpoint

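### Time to first antibiotic modification is a time-to-event outcome, but the SAP gives no rule for children without an event and pools escalation with de-escalation

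*SAP*

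**What the plan says.** SAP, Secondary Outcome Measures, item 2, is "Median time from randomization to first appropriate antibiotic escalation or de-escalation", judged "based on patient's clinical status and available supporting laboratory evidence, or lack thereof, of specific type of infection within 14-days post randomization". The protocol (6.0, Study Outcomes) has the same composite: "time from randomization to first appropriate antibiotic modification (escalation or de-escalation)".

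The SAP names no test for this outcome, so the general rule in F. Analysis Plan applies: "We will compare other continuous outcomes using a Wilcoxon rank-sum test". The display, under 3. Antibiotic Use, is "Time to first antibiotic modification, using the empirical cumulative distribution function"; the word *appropriate* is absent there.

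The same section does fix a value at day 14 for days of therapy: "Patients who are continued on antibiotics longer than 14 days will be assigned a time of 14 days per antibiotic". It repeats this for broad-spectrum and IV therapy, but gives no counterpart for time to modification. The Cox analyses concern time to cessation and the percentage of patients on antibiotics.

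Escalation and de-escalation are defined separately under Definitions. De-escalation includes "Changing to a narrower spectrum antibiotic, cessation of one or more antibiotics".

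**The concern.** A time to first event within a window has three kinds of patient without an observed time: those still unmodified at day 14, those who die first, and those discharged first. The SAP gives follow-up as the hospital stay, capped at 30 days, so discharge can end observation inside the window. A rank-sum test and an uncensored distribution function need a decision on each group, and the SAP makes none. The choice would then fall to the analyst once the data are in hand, and different choices can give different answers.

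The second difficulty is direction. The SAP's stated aim is early and safe de-escalation. The protocol's algorithm recommends de-escalation at low or falling PCT, and continuation or escalation at high or rising PCT. It can therefore change both components, and a shorter time to first change could reflect either one.

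The third is *appropriate*. No assessor, written criterion or masking is given. The judgement rests on the laboratory evidence available, and scheduled PCT results exist in the intervention arm only (protocol, Laboratory Analysis).

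**Working it through.** The documents give no event rate, expected time or power for this outcome, so there is no stated figure to reproduce. What follows is illustration. The only document inputs are the 14-day window and the SAP total of 280, taken as 140 per arm (the equal split is an assumption). All rates are assumed; tests are two-sided at 0.05.

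**Step 1. Non-events dropped or ranked last.** Times among modified children are exponential with mean 2.5 days in both arms, and only the share modified differs (3,000 runs). A test on observed times then compares two identical distributions, so it must reject about 5% of the time whatever the difference in shares. Ranking non-events last recovers that difference.

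| Modified, control vs PCT | Power, dropped | Power, ranked last |
|---|---|---|
| 65% vs 80% | 5% | 60% |
| 85% vs 95% | 4% | 31% |
| 90% vs 95% | 5% | 10% |

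The 4% and 5% entries differ only by simulation error, since √(0.05 × 0.95 / 3,000) = 0.4 percentage points. The loss is large if many children go unmodified and small if few do.

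**Step 2. Early end of observation.** With modification hazard h and discharge-or-death hazard d per day, the share with an observed event by day 14 is h/(h+d) × [1 − exp(−14(h+d))]. Take h = 0.30 in both arms, so there is no true effect.

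- d = 0.03: 0.909 × 0.990 = 0.900, so 10% have no event.
- d = 0.10: 0.750 × 0.996 = 0.747, so 25% have no event.

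With these two values in opposite arms (2,000 runs), the Wilcoxon test rejects in:

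- 22.5% of runs if non-events are dropped (average medians 2.08 vs 1.73 days);
- 26.5% if they are set to 14 days (2.43 vs 2.78 days);
- 29.2% if they are given their last observed time.

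A log-rank test with censoring rejects in 4.3%. The first two rules put the arms in opposite order on the same data. With equal d (0.05 in both arms), every method rejects in 4.4% to 5.3% of runs. Discharge was simulated as unrelated to modification, which favours the log-rank test.

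**Step 3. Faster de-escalation, equal loss.** De-escalation hazard 0.20 vs 0.30, escalation 0.05 and d = 0.05 in both arms. Power is 43% with non-events dropped, 58% with them set to 14 days, and 74% by log-rank.

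**Step 4. Pooling the two directions.** De-escalation/escalation hazards are 0.20/0.05 in one arm and 0.125/0.125 in the other, so the total is 0.25 in both; d = 0.05. The share with an event is 0.25/0.30 × [1 − exp(−4.2)] = 0.833 × 0.985 = 0.821. Escalation comes first in 0.821 × 0.20 = 16% versus 0.821 × 0.50 = 41% (simulated 16.5% and 40.9%). The composite test rejects in only 4% to 6% of runs. A large difference in direction is invisible to it.

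**The case against.** **Non-events may be few.** Stopping one drug counts as de-escalation, so finishing a course is an event. The protocol (10.0) gives an average ICU course of 4 days, and infections needing long courses are excluded. This stands: 65% versus 80% modified is a favourable scenario, and at 90% versus 95% the gap nearly closes. But the documents give no rate, the qualifier *appropriate* could lower it, and discharge before a modification remains possible.

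**The SAP does not say that non-events are dropped.** A reader might infer that it does, because a rank-sum test on recorded times would lose them. But a distribution function over all analysed patients that levels off below one, or a Wilcoxon test ranking non-events last, fits the text equally well. The defect is the missing rule, not a stated exclusion.

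**The composite is deliberate.** It is pre-specified in the protocol, and the algorithm is meant to guide change in both directions. This stands as a reason to keep it. The SAP's stewardship tables do split escalation from de-escalation, but as counts and percentages, not times.

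**Nobody is said to judge *appropriate* with knowledge of the arm.** A reader might infer this from the in-person stewardship rounds in the intervention arm. The documents name no assessor, so the supportable statement is that assessor, criterion and masking are unspecified. Nor are the SAP's definitions free of judgement: the de-escalation definition itself uses the word for an IV-to-oral switch, and no spectrum ranking is given.

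**Conclusion.** The point holds as a gap in one secondary outcome. The SAP sends a 14-day time-to-event outcome to a continuous-data test without saying how children with no modification, death or early discharge enter it. The consequence ranges from slight (5% versus 10% power at 90% versus 95% modified) to serious (5% versus 60% at 65% versus 80%). False-positive rates reach 22% to 29% if early loss differs by arm as assumed here, and stay near 5% if loss is equal. These figures rest on assumed rates, exponential times and 140 per arm, and they show a range of consequences, not a forecast.

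Pooling the two directions means that neither a shorter time nor a null result can be interpreted alone. A reader might go further and conclude that the composite should be replaced or *appropriate* struck out. The documents do not require that: both are in the protocol's pre-specified outcome, and changing them would redefine an endpoint in a study projected to end on June 30, 2019, under a SAP dated June 4, 2019. The primary outcome is not touched.

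**What to change.** Amend the SAP text and leave the protocol composite in place.

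1. Analyse it over all analysed patients as time to event to day 14. Censor children with no event at day 14, treat death as a competing event, and state a rule for discharge before modification. Two workable rules are to censor at discharge, or to count stopping all antibiotics at discharge as de-escalation. The first assumes that discharge is unrelated to the chance of modification; the second needs discharge prescriptions.
2. Replace the empirical distribution function with cumulative incidence curves by arm, and name one test in advance, Gray's or log-rank.
3. Add time to first de-escalation and time to first escalation as separate, competing first events under the SAP definitions.
4. Add a sensitivity analysis counting any modification under those definitions, whether or not judged appropriate, and state which version the figure shows.

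The cost is a few extra analyses of a secondary outcome. No change to the primary analysis or sample size is needed.

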# **Specific Aims**

- 1. Compare antimicrobial utilization among children in the ICU who receive standard-of-care testing plus stewardship vs. PCT-based treatment plus stewardship. We will compare days of antibiotic therapy in the first 14 days following randomization between the study arms. We will test the hypothesis that duration of antibiotic therapy will be 2 days shorter in the group with PCT-guided management vs. the group with standard of care testing and treatment.
- 2. Compare clinical outcomes and safety among children in the ICU who receive standard-of-care testing plus stewardship vs. PCTbased treatment plus stewardship. We will compare mortality, length of stay, recurrence of infection, and antibiotic-associated adverse events (rash, myelosuppression, renal impairment, hepatotoxicity, *C. difficile* infection) between the study arms. We will test the hypothesis that outcomes and safety will be comparable between the study arms.

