Table: Days of antibiotic therapy per patient within 14 days, restricted to patients with a final diagnosis of pneumonia.

Table: Days of antibiotic therapy per patient within 14 days, restricted to patients with sepsis as their indication for antibiotics.

Table: Days of antibiotic therapy per patient within 14 days, restricted to patients with an initial procalcitonin level < 0.5 ng/mL.

Table: Days of antibiotic therapy per patient within 14 days, restricted to patients with an initial procalcitonin level > 0.5 ng/mL.

5. Antimicrobial Stewardship

Table: Number (%) of patients with a stewardship recommendation made within 48-hours of enrollment

Table: Number (%) of stewardship recommendations accepted in each arm

Table: Number (%) of recommendations to de-escalate therapy

Table: Number (%) of recommendations to escalate therapy

Table: Number (%) of recommendations to optimize dose

Table: Number (%) of recommendations to consult the infectious diseases service

Table: Number (%) of recommendations to de-label a beta-lactam allergy

ProPICU: Statistical Analysis Plan

June 4, 2019

Table: Number (%) of recommendations that were not accepted due to provider discretion

Table: Number (%) of recommendations that were not accepted due a patient medication allergy

Table: Number (%) of recommendations that were not accepted due provider waiting for 48-hour culture results

Table: Number (%) of recommendations that were not accepted due to unknown reasons

Table: Number (%) of any antibiotic change that was initiated by pediatric intensive care provider, pediatric infectious diseases provider or stewardship provider

Table: Number (%) of antibiotic escalation that was initiated by pediatric intensive care provider, pediatric infectious diseases provider or stewardship provider

Table: Number (%) of antibiotic de-escalation that was initiated by pediatric intensive care provider, pediatric infectious diseases provider or stewardship provider

6. Clinical Outcomes

Table: Number (%) of death within 30 days of randomizationMedian time from randomization to death among patients who died

Table: Median length of stay within 30 days after randomization

Table: Median length of ICU stay within 30 days after randomization

Table: Number (%) with antibiotic complication

Table: Number (%) with infection with multi-drug resistant organism

Table: Number (%) with hospital re-admission within 30 days

7. Sensitivity analysis

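### Hospital and ICU stay are compared only among children alive at day 30, so if deaths differ between arms and fall among would-be long stayers, the arm with more deaths can appear to have the shorter stay.

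*SAP*

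**What the plan says.** In the SAP's Clinical Outcome Measures, item 2 is "Length of stay in the hospital after randomization, up to 30 days, for those patients alive at 30 days" and item 3 is "Days in the ICU during hospitalization after randomization, up to 30 days, for those patients alive at 30 days". Item 1, listed separately, is "In-hospital mortality within 30 days of randomization".

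The test comes from the Analysis Plan (SAP section F): "We will compare other continuous outcomes using a Wilcoxon rank-sum test, and categorical outcomes using a Pearson's chi-squared test". Neither stay outcome has any rule for death other than exclusion. The analyses headed as sensitivity analyses (SAP items 4 and 7) deal with the primary outcome and with children approached but not enrolled, not with stay.

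Three other places bear on the point:
- SAP section D, the interim look done for safety: "secondary outcomes of 30-day mortality and length of intensive care unit stay will be compared between groups".
- SAP item 6, Clinical Outcomes, has the shell "Table: Median length of ICU stay within 30 days after randomization", with no mention of survivors.
- Protocol 6.0, Study Outcomes, lists "length of ICU stay, length of overall hospital stay, ventilator days", also with no mention of survivors. Specific Aim 2 includes length of stay among the outcomes to which this applies: "We will test the hypothesis that outcomes and safety will be comparable between the study arms".

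**The concern.** Being alive at day 30 is a consequence of what happens after assignment. A comparison restricted to survivors conditions on it, and the balance that assignment provides no longer protects the result. This matters more here than for an ordinary secondary outcome. Protocol 7.0 names stopping antibiotics too early as the risk of the intervention, and stay is one of the outcomes meant to show that less antibiotic does no harm. If harm took the form of extra deaths among the sickest children, removing those children could turn part of the harm into an apparently shorter stay in the same arm. A comparable or shorter stay would then be read as reassurance.

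**Working it through.** **No plan figure to reproduce.** Neither document states an expected mortality, an expected stay or a link between them. The only design calculation concerns antibiotic days. Everything below except the sample size is therefore assumed.

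**Inputs.**
- From the SAP: 280 participants, taken as 140 per arm (an equal split is assumed).
- Assumed: no effect of the intervention on underlying stay; log-normal stay with median 8 days and log-SD 0.8, capped at 30; control mortality 3%; PCT-arm mortality 3%, 6% or 10%. Expected deaths per arm are 140 × 0.03 = 4.2, 140 × 0.06 = 8.4 and 140 × 0.10 = 14.
- Varied: the link between death risk and underlying stay (none, moderate or strong).

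**Step 1: where the shift comes from.** Let m be mortality in an arm, L the mean underlying stay of all its children, and G the amount by which the would-be stay of those who die exceeds L. Since L = (1 − m) × (survivor mean) + m × (L + G),

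survivor mean − L = −G × m/(1 − m).

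With the same L and G in both arms, the survivor difference (PCT minus control) is −G × [m₁/(1 − m₁) − m₀/(1 − m₀)].

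- 3% versus 3%: the bracket is 0, so there is no shift.
- 3% versus 6%: 0.0638 − 0.0309 = 0.0329.
- 3% versus 10%: 0.1111 − 0.0309 = 0.0802.

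If G = 0 the shift is zero at any mortality. If G were negative the sign would reverse.

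**Step 2: simulated survivor differences (PCT minus control, true difference 0).**

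| Link between death and stay | 3% v 6%, mean days | 3% v 10%, mean days |
|---|---|---|
| None | about 0 | about 0 |
| Moderate | -0.13 to -0.17 | -0.35 |
| Strong (one shared severity score) | -0.28 | -0.68 |

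Step 1 agrees: 0.28/0.0329 = 8.5 and 0.68/0.0802 = 8.5. The strong case therefore amounts to children who die having would-be stays about 8.5 days above average. Median differences, which are what the SAP reports, run from 0 to about -0.2 days at 3% versus 6% and from 0 to about -0.4 days at 3% versus 10%.

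**Step 3: effect on the Wilcoxon test.** With equal mortality, about 2–3% of runs show a significantly shorter stay in the PCT arm. At 3% versus 6% the figure is about 2–5%, and where a link exists at 3% versus 10% it is about 4–9%. The run-to-run SD of the mean difference is about 0.9 days.

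**Step 4: would the separate mortality comparison give warning?** For 3% versus 6% at 140 per arm, pooled proportion 0.045, SE = √(2 × 0.045 × 0.955/140) = 0.0248 and 0.03/0.0248 = 1.21, so power is about P(Z > 1.96 − 1.21) = 23% (22% by simulation). At the interim look, with about 70 per arm, it is about 12–13%.

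**The case against.** The best defence is that death is not hidden. In-hospital mortality within 30 days is the first clinical outcome, has its own table together with time to death, and is compared at the interim look in the same sentence as ICU stay. Summaries of continuous variables include the number of participants, so exclusions would show. The restriction also avoids a real artefact: counting days up to death would make an early death look like a short stay. Survivor-only stay beside mortality is a recognisable choice, and these are not primary outcomes.

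Most of this stands. It lowers the stakes but does not restore the comparison, because the mortality test would usually miss an imbalance such as 3% versus 6%. A non-significant mortality result beside an unremarkable or shorter stay is a plausible outcome of the plan as written.

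Three stronger readings are tempting, and the documents do not support them:
- *That the restriction necessarily favours the arm with more deaths.* This needs children who die to be those who would have stayed long. That is plausible, but neither document says it.
- *That a death-inclusive result in the opposite direction measures the error.* In the strong case at 3% versus 6%, scoring deaths as 30 days gives +0.33 days against -0.28 in survivors. The true stay difference in that simulation is 0; the +0.33 is largely the mortality difference expressed in days.
- *That the SAP tables contradict the definitions.* The shells are short titles. Omitting a restriction defined earlier does not revoke it, and section D does not say which population the interim comparison uses.

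**Conclusion.** The concern holds in a conditional form. As written, two listed safety outcomes are compared in groups selected on a post-randomisation outcome, and no analysis of stay in all participants is planned. That does not depend on any assumed number.

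The direction and size of the bias do. If mortality differs and deaths fall among would-be long stayers, the arm with more deaths can look as if it has a shorter stay: about 0 to -0.3 mean days (0 to -0.2 median days) at 3% versus 6%, and about 0 to -0.7 mean days (0 to -0.4 median days) at 3% versus 10%. The upper ends need death and stay to be driven by the same severity. With equal mortality and the same link in both arms, or with deaths unrelated to stay, the survivor difference is about zero, although the analysis then ignores the deaths. These shifts are smaller than the chance variation of about 0.9 days, so the survivor restriction should not be described as likely to produce a false significant result. It should be changed because the comparison supports a safety claim and the change is cheap.

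**What to change.** Reword Clinical Outcome Measures 2 and 3 so that the between-arm comparison uses all participants in the analysis population. Choose one of these in advance:
- ICU-free and hospital-free days to day 30, with death scored 0; or
- stay to day 30 in the Wilcoxon test already planned, with death given the worst rank.

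The first ties deaths with children still in the unit or hospital at day 30, while the second ranks deaths below them; the SAP should say which is intended. Simply dropping the survivor restriction and counting days to death is not a fix, because early death would then shorten stay.

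Keep the survivor-only median (Q1–Q3) as a descriptive summary next to mortality. Apply the same definition to the interim ICU-stay comparison in SAP section D and to the item 6 tables. Because the SAP's mortality outcome is in-hospital, also state how vital status to day 30 is established for children discharged earlier.

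The cost is SAP wording, with no change to enrolment or design. The downside is a composite that is slightly harder to read and partly reflects mortality, which is why the descriptive survivor summary and the separate mortality result should stay beside it.
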